Prosthetic fabrication. Participants will coordinate with *** for fabrication of a duplicate prosthesis that incorporates the study foot that the participant does not currently own (either a low-profile foot, Össur Flex-Symes or a high-profile crossover foot, Össur Cheetah Xplore).

Baseline assessment and verification of equivalence. Once the study prosthesis is finalized, participants will be invited to the Amplifying Mobility and Performance (AMP lab) to collect baseline information and assess the two prostheses for equivalence. A self-report survey of basic demographic and health questions and standardized health instruments will then be administered to characterize the sample at baseline. Then, a study prosthetist will verify fit, alignment, function, and equivalence of the study prostheses. If study prostheses are determined to be equivalent, the participants will be randomly assigned to one prosthetic condition to use exclusively for a period of two weeks. Study researchers will retain the other prosthesis to ensure full time use of the assigned prosthesis.

First data collection session. After two weeks of use, participants will return to the AMP lab for assessment of walking performance and self-reported health outcomes in the first assigned prosthetic condition. Participants will be fit with retroreflective markers and asked to walk at their self-selected slow, comfortable, and fast speeds over force plates until a minimum of 10 clean captures are collected for both the prosthetic and sound side. Marker position will be captured using a 10-camera Qualisys motion capture system; force date will be collected over a series of four Kistler instrumented force plates. After data collection, the participant will switch to the second prosthetic conditions for use over a two-week period. During this period, the first prosthesis will remain with study researchers.

Second data collection session. After two weeks of use, participants will return to the AMP lab for assessment of walking performance and self-reported health outcomes in the second prosthetic condition. Following gait data collection, a qualitative interview will be conducted, where participants will be asked which prosthetic foot they preferred overall, and their experience using both prostheses for various daily activities.

(5.2)MRI scans. Will any subjects have a Magnetic Resonance Imaging (MRI) scan as part of the study procedures?

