BMIC Biomolecular Imaging Center (South Lake Union research facility)

	Harborview Radiology/Imaging Services (the Harborview clinical facility)		
	SCCA Imaging Services		
	Northwest Diagnostic Imaging		
	Other: identify in the text box below:		

Personnel. For MRI scans that will be conducted at the DISC or BMIC research facilities: The role, qualifications, and training of individuals who will operate the scanner, administer the GBCA (if applicable), and/or insert and remove the IV catheter should be listed on the Study Team addendum.

5.3 Data variables. Describe the specific data you will obtain (including a description of the most sensitive items). If you would prefer, you may upload a list of the data variables to the **Supporting Documents** SmartForm instead of describing the variables below.

Biomechanical parameters. Three-dimensional position and force data will be collected and used to calculate the following gait parameters: step length asymmetry (i.e., the difference between prosthetic and sound side step lengths), prosthetic ankle range of motion (i.e., the total angular motion of the ankle in the sagittal plane during stance phase), prosthetic-side energy return (i.e., intersegmental flow of power out of the prosthesis), and peak sound-side limb loading (i.e., maximum vertical ground reaction force in early stance).

Patient-reported measures and interviews. To assess patient perspectives, a survey of standardized self-reported health outcomes will be administered at each visit. The survey will inquire about mobility (Prosthetic Limb Users Survey of Mobility, PLUS-M, 12-item Short Form version 1.2), balance confidence (Activities-Specific Balance Confidence Scale, ABC), functional and aesthetic satisfaction (Trinity Amputation and Prosthesis Experience Scales- Revised, TAPES-R-AES, TAPES-R-FUN), and activity restrictions (TAPES-R-AR). At the end of the study, participants will engage in a qualitative interview with closed- and open-ended questions to elicit preferences and experiences with both feet.

Variables to characterize the sample. A self-report survey including basic demographic (e.g., age, sex) and health questions (e.g., amputation etiology, time since amputation, hours of prosthesis use per day) will be administered at baseline. Participants will also be asked about socket comfort at each appointment using the Socket Comfort Scale (SCS) measures of current, best, worst, and average comfort.

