## Data analysis plan

Variables that characterize the study sample. Summary statistics (i.e., means, standard deviations) will be calculated for all demographic and clinical characteristics. A paired t-test ( $\alpha$ =.05) will be used to assess whether SCS statistically differs between foot conditions to examine prosthetic comfort equivalence.

Biomechanical and self-reported health outcome variables. Biomechanical data will be assessed for quality using Qualisys Track Manager to identify markers, interpolate gaps, and truncate trials to data collected in the capture volume. Visual 3D software (C-Motion, Inc., Rockville, MD) will be used to filter data, build models, label gait events, and compute outcomes. Self-reported data will be scored according to developer instructions. All data will be assessed for adherence to statistical assumptions. If sufficiently normal, paired t-tests will be used to assess statistical difference between all biomechanical and health outcome variables ( $\alpha$  =.05). Adjustments for multiple comparisons will not be applied due to the pilot nature of the study. Prosthetic foot preference will be reported as percentages; participant qualitative comments will be compiled and reviewed to inform study findings and future research directions.

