## Note:

Due to the advent of COVID-19, the goal number of participants (10) was not achieved. While five (5) participants were recruited, data was only collected for two (2) prior to cessation of human subjects research. As a result, inferential statistical analysis was not possible, and summary statistics (i.e., means, standard deviations) were used to compare prosthetic foot conditions for both participants.

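### Does the missing sign and averaging rule for step length asymmetry call for a change to the plan?

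*Protocol*

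**What the plan says.** Protocol section 5.3 gives the outcome a one-phrase definition: "step length asymmetry (i.e., the difference between prosthetic and sound side step lengths". The other three gait parameters there (ankle range of motion, energy return and sound-side loading) are described as briefly.

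Under the first data collection session in Protocol section 5.1, participants are "asked to walk at their self-selected slow, comfortable, and fast speeds over force plates", and walking continues "until a minimum of 10 clean captures are collected for both the prosthetic and sound side". There is no rule for pairing left and right steps or for averaging captures.

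The SAP's Data analysis plan adds no formula. It says that Visual 3D "will be used to filter data, build models, label gait events, and compute outcomes", and that, if the data are sufficiently normal, "paired t-tests will be used to assess statistical difference between all biomechanical and health outcome variables".

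The SAP Note then reports that "the goal number of participants (10) was not achieved" and that "data was only collected for two (2) prior to cessation of human subjects research". Inferential analysis was therefore not possible, and "summary statistics (i.e., means, standard deviations) were used to compare prosthetic foot conditions for both participants".

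**The concern.** A difference between two sides can be a signed number, whose direction shows which leg takes the longer step, or a magnitude. The two answer different questions. Signed values can cancel when people lean in opposite directions. Magnitudes cannot cancel, but step-to-step variation pushes them upward and they hide a change of direction. If magnitudes are used, it also matters whether they are taken for each step pair or after averaging the steps on each side.

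The SAP Note says that means and SDs were reported, but not what the SD is taken over. With two participants those summaries are the whole quantitative comparison. A reader without the formula might not know whether a value is a directional shift, a size of asymmetry, or a size inflated by noise.

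**Working it through.** The plan states no figure to reproduce: the documents give no step lengths, SDs or expected effect for this outcome. The only inputs from the documents are 10 captures per side (Protocol section 5.1) and two participants with data (SAP Note). All other values below are assumptions, and steps are taken as independent.

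**1. Signed values.** With equal numbers of steps per side, mean(Pᵢ − Sᵢ) = mean(P) − mean(S), so pairing and averaging first give the same mean. The protocol sets a minimum of 10 captures, so equal counts are themselves an assumption. Reversing the subtraction changes the sign for both feet and leaves the size of the foot contrast, and any two-sided p-value, unchanged. Only the SD differs: signed step pairs have SD √2·s (2.83 cm for a step SD s of 2 cm), whereas a single difference of averages has no step-level SD.

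**2. Absolute values within one participant.** If the per-pair asymmetry is N(μ, σ²) with σ² = 2s², the mean absolute value is σ·√(2/π)·exp(−μ²/2σ²) + μ·[1 − 2Φ(−μ/σ)]. Averaging 10 steps per side first replaces σ² by 2s²/10.

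Take μ = 1 cm, s = 2 cm (σ² = 8), and a second foot that halves μ:

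| Reading | First foot, mean (SD) | Second foot, mean (SD) | Contrast |
|---|---|---|---|
| Signed | 1.00 (2.83) | 0.50 (2.83) | 0.50 |
| Absolute per step pair | 2.40 (1.80) | 2.29 (1.73) | 0.10 |
| Absolute after averaging | 1.12 | 0.82 | 0.30 |

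The per-step magnitude keeps about 21% of the contrast here. The result depends heavily on the assumptions, as these shares kept under halving show:

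| Step SD | μ = 1 cm | μ = 2 cm | μ = 4 cm |
|---|---|---|---|
| 1 cm | 40% | 70% | 95% |
| 2 cm | 21% | 40% | 70% |
| 3 cm | 14% | 28% | 52% |

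Averaging first at s = 2 cm keeps 0.89 of 1.00 cm at μ = 2 and 1.99 of 2.00 cm at μ = 4.

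**3. Pooling the two participants, no noise, second foot halves the asymmetry.**

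- +4 and −4 cm: signed means 0 v 0; absolute means 4 v 2.
- +4 and −2 cm: signed 1.0 v 0.5; absolute 3.0 v 1.5.
- +4 and +2 cm: 3.0 v 1.5 either way.

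Cancellation needs opposite leans. If a share p of people lean one way, the chance of this for two people is 2p(1 − p): 50%, 42%, 18% and 0% for p = 0.5, 0.7, 0.9 and 1.0.

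**4. Which case the documents point to.** Section 5.3 names two sides and a difference and says nothing of magnitude, so it reads as signed. The Note's summaries cover both participants, which reads as results for each of the two. Under those readings step 1 applies, and the losses in steps 2 and 3 do not arise.

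**The case for a change.** The case for asking for a change is that it would cost one line. The descriptive values are all that the study has, so their meaning should be beyond doubt. A signed reading still leaves the direction unstated, and an SD within one person needs several asymmetry values, so the unit of the SD is open on any reading. If the two participants were pooled, the choice could even reverse the comparison: one foot at +4 and −4 cm and the other at +1 and +1 cm gives a difference in means of −1.0 signed and +3.0 absolute. Protocol section 5.11 also foresees later comparisons with other amputation levels, for which the formula must be known.

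Much of this stands as advice on reporting. A results table should give the order of subtraction and say what the SD covers. It does not show that the planned definition is wrong or that another would be better. Signed values can cancel between people; absolute values turn a reversal from +1 to −1 cm into no change. Section 5.11 provides for keeping the de-identified biomechanical data, so either form should remain computable. Prescribing that steps be averaged first would be a preference, and it would remove the step-level SD.

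**Conclusion.** No change to the plan follows. This is a gap in detail that a gait analyst fills in the ordinary way, with a signed difference for each participant and foot. On that reading the mean does not depend on how steps are combined, apart from small effects of unequal step counts, and nothing cancels between people.

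The large distortions, down to 14% of the contrast kept under halving, need absolute values per step together with an asymmetry near 1 cm and step variation of 2 to 3 cm. Neither document suggests that combination. No test was run, and no conclusion stated in the documents depends on the choice.

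This rests on reading section 5.3 as signed and the SAP Note as per participant. Both are the plainer readings, but the text available does not state either. If the report pooled the two people or used magnitudes, its own labelling would need to say so.

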## Data analysis plan

Variables that characterize the study sample. Summary statistics (i.e., means, standard deviations) will be calculated for all demographic and clinical characteristics. A paired t-test ( $\alpha$ =.05) will be used to assess whether SCS statistically differs between foot conditions to examine prosthetic comfort equivalence.

Biomechanical and self-reported health outcome variables. Biomechanical data will be assessed for quality using Qualisys Track Manager to identify markers, interpolate gaps, and truncate trials to data collected in the capture volume. Visual 3D software (C-Motion, Inc., Rockville, MD) will be used to filter data, build models, label gait events, and compute outcomes. Self-reported data will be scored according to developer instructions. All data will be assessed for adherence to statistical assumptions. If sufficiently normal, paired t-tests will be used to assess statistical difference between all biomechanical and health outcome variables ( $\alpha$  =.05). Adjustments for multiple comparisons will not be applied due to the pilot nature of the study. Prosthetic foot preference will be reported as percentages; participant qualitative comments will be compiled and reviewed to inform study findings and future research directions.

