5 PROCEDURES

5.1 Study procedures. Using lay language, provide a complete description of the study procedures, including the sequence, intervention or manipulation (if any), drug dosing information (if any), use of records, time required, and setting/location. If it is available and you think it would be helpful to the IRB: Upload a study flow sheet or table to the **Supporting Documents** SmartForm in **Zipline**.

For studies comparing standards of care: It is important to accurately identify the research procedures. See UW IRB POLICY:
Risks of Harm from Standard Care and the draft guidance from the federal Office of Human Research Protections, "Guidance on Disclosing Reasonably Foreseeable Risks in Research Evaluating Standards of Care"; October 20, 2014.

The proposed pilot randomized crossover study will assess biomechanical gait parameters, self-reported health outcomes, and qualitative feedback in participants with Syme's amputation under two prosthetic foot conditions: (1) a traditional low-profile Syme's foot, and (2) a high-profile crossover foot. Participants will already own a high-profile crossover foot or a low-profile energy storing foot. An additional prosthesis with the other study foot and an equivalent socket will be fabricated by the participant's certified prosthetists to facilitate unique socket attachment requirements. The order in which the participants will receive the prostheses will be randomly assigned. Participants will be instructed to wear the assigned prosthesis for at least two weeks prior to data collection to experience the function of the prosthetic foot under a variety of environments and activities. After each period of wear, biomechanical data will be collected for the respective prosthetic condition. Participant perspectives of the prosthetic feet will be assessed through a standardized self-reported measures and a qualitative semi-structured interview.

Screening and consent. Interested participants will be screened for study eligibility via telephone interview. Eligible participants will be sent a consent form via email or mail for their review. At a later time, the study will be explained in detail over the phone and verbal consent will be obtained.

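### Socket-comfort equivalence is examined with a test for a difference and no margin; at the goal of 10, true gaps below about 0.7 SD of the within-person differences (two-sided test) would be non-significant more often than not, and that would not show equivalence

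*SAP*

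**What the plan says.** The SAP (Data analysis plan, paragraph on variables that characterize the sample) specifies one analysis of socket comfort: a paired t-test at alpha .05, which "will be used to assess whether SCS statistically differs between foot conditions to examine prosthetic comfort equivalence". Neither the SAP nor the protocol gives an equivalence margin, a confidence-interval criterion or an equivalence test for SCS.

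Protocol section 5.3 (Data variables) says comfort is recorded at each appointment "using the Socket Comfort Scale (SCS) measures of current, best, worst, and average comfort". That makes four scores, and the SAP does not say which one is tested.

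Protocol section 5.1 also has a check before randomization, in which "a study prosthetist will verify fit, alignment, function, and equivalence of the study prostheses". No numeric criterion is attached to it. On who brings which prosthesis, the same section says: "Participants will already own a high-profile crossover foot or a low-profile energy storing foot". The other prosthesis is newly made for the study.

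The SAP's closing Note records that "the goal number of participants (10) was not achieved", that data were collected for two participants, and: "As a result, inferential statistical analysis was not possible".

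**The concern.** A paired t-test takes no difference as its null hypothesis. Failing to reject it can mean that the difference is small, or that the sample was too small to see it. Without a margin, the result cannot tell these apart. The SAP names equivalence as the aim and offers no other statistical route to it, so the natural reading is that a non-significant result would count in favour of equivalence.

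This matters because each participant compares an owned prosthesis with a newly made one. If comfort differs between the sockets, it competes with the foot as an explanation for differences in gait, satisfaction and preference. The new socket is not tied by design to one foot, since participants may own either at entry, but in a small sample ownership need not balance across feet. Reporting a non-significant SCS test as equivalence would give more reassurance than the data hold.

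The unnamed score adds to the problem: with four SCS scores available, the one reported could be chosen after the data are seen.

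**Working it through.** The plan gives no power, effect size, SD or margin for SCS, so there is no figure of its own to reproduce. The check asks how a non-significant result behaves at the planned size.

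**Inputs**
- n = 10 paired differences (goal, SAP Note); n = 2 obtained (same Note).
- Alpha = .05 (SAP, Data analysis plan). Sidedness is not stated; two-sided is assumed.
- Assumed: normal within-person differences. All gaps and margins are in units of the SD of those differences, because the documents give no SD in SCS points. The margins used below are illustrations.

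**1. How often the planned test is non-significant when a gap exists.** With true gap d, the t statistic is noncentral t with n − 1 = 9 degrees of freedom and noncentrality d√10. The critical value is t(.975, 9) = 2.262.

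| True gap d (SD) | d√10 | P(non-significant) |
|---|---|---|
| 0.3 | 0.95 | 86% |
| 0.5 | 1.58 | 71% |
| 0.694 | 2.19 | 50% |
| 0.8 | 2.53 | 38% |
| 1.0 | 3.16 | 20% |

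Gaps below about 0.69 SD are therefore missed more often than not; larger ones are usually detected.

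Sensitivity of the even-odds point:
- A one-sided test at .05 gives 0.56 SD.
- In units of the per-condition SD, it is 0.69 × √(2(1 − r)), where r is the correlation between conditions. This gives 0.98 for r = 0, 0.69 for r = 0.5 and 0.54 for r = 0.7. The documents give no r.

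**2. Precision.** The 90% CI half-width, taking the sample SD as the unit, is t(.95, n − 1)/√n.
- n = 10: 1.833/√10 = 0.58 SD.
- n = 2: 6.314/√2 = 4.46 SD.

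**3. What a non-significant result implies when comfort is truly identical.** In 400,000 simulated trials of n = 10 with zero true difference, 95% are non-significant, as they should be. The second column below gives the share of those whose 90% CI still extends beyond the margin.

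**4. What an equivalence test could do.** Equivalence is declared when the 90% CI lies wholly inside ± the margin (two one-sided tests at 5% each). Power is at zero true difference.

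| Margin (SD) | Non-significant, but CI extends beyond margin | Equivalence power, n = 10 | n for 80% power |
|---|---|---|---|
| 1.0 | 18% | 80% (0.795) | 11 |
| 0.75 | 55% | 43% | 17 |
| 0.5 | 93% | 7% | 36 |

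Even with identical comfort, then, a non-significant t-test often leaves differences larger than the margin unexcluded, and increasingly so as the margin tightens.

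**The case against.** The strongest case against is about weight. The test was never run, and neither document reports a conclusion of comfort equivalence. The SAP speaks of examining equivalence, not establishing it, and does not write down that non-significance means equivalence. A significant result would have been a legitimate warning. Both documents class SCS as a variable describing the sample, and the operative gate is the prosthetist's check, which must be passed before assignment. No SCS standard deviation or margin exists to show that a clinically important gap would be missed. An equivalence test at 10 participants would usually return "not shown" unless the margin were wide.

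Much of this stands. The decision rule is inferred from the purpose clause. The consequence for this study is limited to how comfort is described. The documents cannot settle whether an important gap would usually be missed.

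Two parts do not remove the point. The prosthetist's check has no numeric criterion and precedes the two-week wear periods, so it cannot stand in for comfort as experienced during wear. And low power for equivalence is no reason to rely on a difference test: it means that 10 participants carry little evidence on equivalence, which the plan should acknowledge.

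**Conclusion.** The concern holds. The stated analysis cannot deliver its stated purpose, because a non-significant paired t-test with no margin is not evidence of equivalent comfort. At the goal of 10, with a two-sided test and normal differences, true gaps below about 0.69 SD of the within-person differences would be non-significant more often than not.

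Confidence is high on the logic and on these figures in SD units. What they mean in SCS points is unknown. With the two participants obtained, no equivalence analysis is useful. The point should be fixed, but its reach is confined to the wording of this study's report and to any reuse of the plan.

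**What to change.** **For this study.** Report each participant's SCS scores by foot condition beside the outcomes, state which prosthesis was the newly made one, and do not claim comfort equivalence. This costs only wording.

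**For the plan as designed for 10, or a restart.** Replace the SCS sentence with text such as:

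> One SCS score, named before data collection, will be compared between foot conditions as the mean paired difference with its 90% CI. Comfort equivalence will be claimed only if the CI lies inside a margin in SCS points fixed before data collection. The other SCS scores will be reported descriptively.

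If no margin can be justified, which may well be the case for a pilot, delete the equivalence phrase and report the paired difference with its CI.

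The cost is one named score and one margin, with no added measurements. The drawback is that at 10 participants equivalence will often be reported as not shown, unless a margin of about 1.0 SD of the differences is acceptable.

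### The SCS comfort check is made only by foot type, so with mixed ownership a consistent owned-versus-duplicate socket difference partly or wholly cancels (minor)

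*SAP*

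**What the plan says.** The SAP (Data analysis plan, first paragraph) assigns one analysis to the Socket Comfort Scale (SCS): a paired t-test at 0.05 to "assess whether SCS statistically differs between foot conditions to examine prosthetic comfort equivalence". It gives no equivalence margin, no contrast of owned against duplicate prosthesis, and no term for ownership.

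Protocol 5.1 sets up the pairs. "Participants will already own a high-profile crossover foot or a low-profile energy storing foot", and "An additional prosthesis with the other study foot and an equivalent socket will be fabricated". The paragraph on prosthetic fabrication confirms that the new device is the one with the foot the participant lacks; participants arrange "for fabrication of a duplicate prosthesis that incorporates the study foot that the participant does not currently own". The ownership split is neither fixed nor reported.

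There is also a check on each pair before randomisation. At the baseline visit "a study prosthetist will verify fit, alignment, function, and equivalence of the study prostheses", and "If study prostheses are determined to be equivalent, the participants will be randomly assigned to one prosthetic condition". No criteria for that judgement are given.

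Protocol 5.3 has SCS collected at every appointment in four forms (current, best, worst, average). The SAP does not say which form is tested. The SAP Note gives a goal of 10 participants, data for two, and summary statistics in place of inferential tests.

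**The concern.** Two comparisons can be made from the same SCS data. One is by foot, high-profile against low-profile. The other is by device history, owned socket against duplicate socket. They coincide only if everyone owns the same foot.

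The sockets are where a comfort mismatch is most likely to arise, because one is established and the other newly made. For an owner of the low-profile foot, high minus low is duplicate minus owned. For an owner of the high-profile foot, it is owned minus duplicate. If duplicates are consistently a little less comfortable, the two groups pull the by-foot mean in opposite directions, and the sign changes also widen its spread.

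At stake is what a non-significant SCS result may be taken to mean. It could be read as showing that paired sockets were equally comfortable when it cannot show that. Under mixed ownership, a real mismatch would add noise to any comfort-sensitive paired outcome and could colour an individual's stated preference, even where the average foot contrast is not shifted.

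**Working it through.** **Inputs from the documents.** Planned n = 10 (SAP Note); paired t-test at 0.05, sidedness not stated (Data analysis plan); either foot may be owned (Protocol 5.1). The plan has no SCS effect size, SD, margin or power figure, so there is nothing of its own to reproduce.

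**Assumptions.** Two-sided test; owned minus duplicate = m + e, with m the consistent mismatch and e normal with mean 0. Main illustration: m = 2 points, SD of e = 1.5. No true effect of foot on comfort.

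**Expected by-foot difference.** With k of 10 participants owning the less commonly owned foot, and up to overall sign,

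E(by-foot difference) = m × (10 − 2k)/10.

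**Noise-free check (every pair differs by exactly 2).** The sample variance is (10/9) × (4 − mean²) and t = mean / √(variance/10). At 8:2, the mean is 2 × 6/10 = 1.2, the variance (10/9) × (4 − 1.44) = 2.84, and t = 1.2/√0.284 = 2.25, so p = 0.051 on 9 df. The last two columns below come from 200,000 simulated trials with SD 1.5.

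| Split | Expected by-foot difference | Noise-free p | By-foot test detects | Owned minus duplicate detects |
|---|---|---|---|---|
| 5:5 | 0 | 1.00 | about 0.1% | 96% |
| 6:4 | 0.4 | 0.56 | 0.7% | 96% |
| 7:3 | 0.8 | 0.22 | 5% | 96% |
| 8:2 | 1.2 | 0.051 | 25% | 96% |
| 9:1 | 1.6 | 0.003 | 66% | 96% |
| 10:0 | 2.0 | not defined (no spread) | 96% | 96% |

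At 5:5 the rate falls below 5% because the sign changes inflate the spread: √(1.5² + 2²) = 2.5 points against 1.5.

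**Other assumed values.** With m = 2 and SD 1, by-foot detection is about 0% at 5:5, 32% at 8:2 and 89% at 9:1, against more than 99% for owned minus duplicate. With m = 1 and SD 2, it is 3% at 5:5 and 11% at 8:2, against 29%. The direction does not change.

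**What an equivalence margin would do.** At 5:5 with m = 2 and SD 1.5, two one-sided tests on the by-foot difference declare equivalence in 0.5% of trials with a 1-point margin, 18% with 1.5 and 67% with 2. A tight margin gives real protection here because the inflated spread makes the test hard to pass. A margin as wide as the mismatch does not.

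**Mismatches in both directions.** If each pair's mismatch is +2 or −2 at random, the by-foot and owned-minus-duplicate tests both reject in about 5% of trials. Neither mean sees this; only the individual values do.

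**The two participants with data.** If they own different feet, any consistent m contributes (m − m)/2 = 0 to the mean foot difference. If they own the same foot, m is fully confounded with foot. The documents do not say which applies.

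**The case against.** Three arguments on the other side carry weight.

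First, socket equivalence does not rest on the SCS test. A prosthetist verifies each pair, and only pairs judged equivalent go on to randomisation. A reader might infer from the table that a trial could report equivalence with no equivalent pair in it. That would need all 10 pairs to pass this check wrongly, in the same direction, and the documents give no reason to expect it. What remains is that the check has no stated criteria and precedes the two-week wear, so it lowers the risk without answering what the SCS data could answer.

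Second, the SAP does not say that its test is about owned and duplicate sockets. Read as a check on whether comfort could bias the foot comparison, the by-foot contrast is the right one: its expected shift, m × (10 − 2k)/10, is the mismatch's contribution to the mean comfort difference between feet, and it is zero when ownership is balanced. The foot may itself also affect comfort. This stands, and it is why the contrast should be kept.

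Third, no inferential test was run. A reader might infer that a false equivalence conclusion has been reported, but the documents report none, and the Note does not say how SCS was summarised.

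Nor do the figures support saying that a margin cannot help, or that owned minus duplicate cures everything. A tight margin does help, mismatches in both directions escape either mean, and at 10:0 the added contrast equals the planned one up to sign.

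**Conclusion.** The concern holds in a limited form. A non-significant by-foot SCS test does not show that the paired sockets were equally comfortable, because under mixed ownership a consistent owned-versus-duplicate difference cancels wholly (equal split) or partly (unequal split). With a single type of owner it is visible but cannot be separated from foot. Separately, under any split, non-significance without a margin does not establish equivalence.

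Under the main illustration, detection runs from about 0.1% at 5:5 to 96% at 10:0, against 96% for owned minus duplicate throughout. These figures rest on an assumed mismatch and SD and on an ownership split that the documents do not give. The sign change itself follows from the design alone.

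Severity is minor: this is a secondary check in a pilot, partly covered by the prosthetist's verification, and its planned test was not carried out.

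**What to change.** In the SAP's paragraph on sample characteristics:

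- Keep the by-foot SCS contrast, described as a check on whether comfort could bias the foot comparison.
- Add SCS on the owned prosthesis minus SCS on the duplicate, as a mean with 95% CI if the planned sample is reached.
- List each participant's SCS pair and absolute difference, since mismatches in both directions cancel in either mean.
- Report how many participants owned each foot, and name the SCS rating used.

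For the two participants with data, show each person's SCS labelled by foot and by owned or duplicate, beside that person's other results, and draw no equivalence conclusion from a by-foot mean. A CI is not worth giving at n = 2: its half-width is 12.706/√2 ≈ 9.0 times the SD, or about ±13.5 points at SD 1.5.

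The cost is a few lines of text and a recode. SCS is taken at each appointment, and which foot each person owned had to be known to make the duplicate. No new measurement is needed.
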